2.3.2 Potential Benefits

Participants may or may not receive benefit from the use of Erenumab in pain reduction and improved function. Additionally, if Erenumab proves to be effective, this will be the first pharmacological approach specifically indicated for TMD with a clear mechanism of action and will provide a novel therapeutic approach to fulfill this highly unmet medical need, changing current management paradigms for the patients suffering of chronic TMD.

3 OBJECTIVES

3.1 Study Objectives

Primary Objective

To investigate the efficacy of Erenumab compared to placebo in the reduction of pain scores in participants with chronic TMD during a 12-week treatment period.

Secondary Objectives

To determine the efficacy of Erenumab on the proportion of subjects with at least 50% reduction from baseline in mean monthly TMD pain days.

To determine the efficacy of Erenumab using functional measures and pain related behaviors: Jaw function, Pressure Pain Thresholds, Oral Behaviors, changes in pain intensity and pain related disability, perspective of pain improvement, and anxiety and depression.

Exploratory Objectives

To explore changes in pro-inflammatory and anti-inflammatory cytokines from plasma/serum.

3.2 Study Outcome Measures

3.2.1 Primary

The primary endpoint will be a monthly mean pain intensity score change from baseline, representing the arithmetic mean of daily average pain intensity score values. The daily average pain intensity score will be measured on a 0-100 numeric rating scale (NRS) and reported in the Daily Symptom Diary (DSD). The monthly mean pain intensity score will be determined from baseline, for each month/cycle (4 weeks/28 days) during the 12 weeks (3 cycles) of treatment and the last month prior last visit (Follow up).

The monthly mean pain intensity score will be calculated if a participant has at least 80% compliance with the DSD.

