5.5.2 Handling of Subject Withdrawals or Subject Discontinuation of Study Intervention

Participants withdrawn after randomization will not be replaced. Participants who are withdrawn voluntarily or by the investigator will be discontinued from the study.

Study staff will complete a study disposition form in the eCRF, indicating the reason for discontinuation.

If the patient is a patient from the school and/or is interested in following TMD care at the Brotman Facial Pain clinic, will be referred to the faculty practice clinic front desk for information and to schedule an appointment if wants to.

Unblinding, if required, will be carried out according to the procedures described in

Section 5.4.2. A participant who has an AE at the time of discontinuation will be followed until the event returns to baseline, resolves, or is stabilized. If the AE does not meet one of these outcomes within 30 days after discontinuation or the end of the study, the participant will be referred to an appropriate provider for continued medical care (See section 9.2).

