7.3.2 Visit 2, 2nd treatment/cycle (Day 28/ 4 weeks after Visit 1)

- Review Daily Symptom Diaries in eCRF or collect and review it in paper forms
- Assess compliance with Daily Symptom Diaries
- Review medical history
- Record concomitant medications and therapies
- Take blood pressure and collect weight
- Administer the Symptom Inventory
- Assess and record adverse events (AEs)
- Perform TMD examination
- Perform Pressure Pain examination
- Perform urine pregnancy test (in women of childbearing potential)
- Review 6 questionnaires from Visit 1 in eCRF or collect and review the paper forms
- Provide instruction to complete 6 new outcome measure questionnaires in paper or electronically for review at Visit 3.

- Provide instruction to complete Daily Symptom Diaries electronically or provide them in paper forms
- Deliver the injection of the study drug or placebo
- Schedule next visit

7.3.3 Visit 3, 3rd and final treatment cycle (Day 56/ after 4 weeks from Visit 2)

- Review Daily Symptom Diaries in eCRF or collect and review it in paper forms
- Assess compliance with Daily Symptom Diaries
- Review medical history
- Record concomitant medications and therapies
- Take blood pressure and collect weight
- Administer the Symptom Inventory
- Assess and record adverse events (AEs)
- Perform TMD examination
- Perform Pressure Pain examination
- Perform urine pregnancy test (in women of childbearing potential)
- Review 5 questionnaires from Visit 2 in eCRF or collect and review the paper forms
- Provide instruction to complete 6 new outcome measure questionnaires in paper or electronically for review at Visit 4.
- Provide instruction to complete Daily Symptom Diaries electronically or provide them in paper forms
- Deliver the injection of the study drug or placebo
- Schedule next visit

7.3.4 Visit 4, assessment of last treatment cycle (Day 84/4 weeks after Visit 3)

- Review Daily Symptom Diaries in eCRF or collect and review it in paper forms
- Assess compliance with Daily Symptom Diaries
- Review medical history
- Record concomitant medications and therapies
- Take blood pressure and collect weight
- Administer the Symptom Inventory
- Assess and record adverse events (AEs)
- Perform TMD examination
- Perform Pressure Pain examination
- Collect blood for Cytokine release assay
- Perform urine pregnancy test (in women of childbearing potential)
- Review 5 questionnaires from Visit 3 in eCRF or collect and review the paper forms
- Schedule next visit

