The Pressure Pain Threshold (PPT) will be defined as the amount of pressure at which the participant first perceives pressure to be painful. The PPT measurements will be performed by trained staff using a pressure algometer (Wagner, Greenwich, CT). Calibrated pressured will applied bilaterally over the masseter, temporalis, upper trapezius, the TMJs, and the lateral epicondyles. One pre-trial assessment will be performed at each anatomic structure followed by additional assessments until 2 measures differing by less than 0.2 kg are obtained, or 5 assessments are administered. In either case, the mean of the 2 closest values will be recorded as the threshold estimate. Pressure stimuli will be delivered at an approximate rate of 1 kg/s. The cutoff pressure for all sites will be 5 kg. The values from the right and left sides will be averaged to obtain a single PPT value per anatomical site [34, 35].

- **Daily Symptom Diary**

Participants will be asked to complete the Daily Symptom Diary at the end of each day during the baseline phase and during the study (visits 1-5).

Participants should have at least 80 % compliance with the DSD.

The diary collects the participant's pain intensity (reported on a 0-100 numeric rating scale) and duration (reported on a 0-100 percentage scale), pain days and use of pain medication. Participants are required to complete a Daily Symptom Diary electronically or on paper and a new form will be used for each month of the study. These forms may be returned in person at study visits.

Outcome Measure Questionnaires

Listed in the Schedule of Events (Appendix A). Questionnaire forms on paper will be provided to the participants if an electronic form is not feasible.

Some questionnaires are self-administered, and others will be administered by trained study staff.

- Jaw Functional Limitation Scale. This is a 20-item instrument that measures limitations across 3 domains related to TMJ biomechanics: masticatory function (6 items), vertical jaw mobility/jaw opening (4 items), and verbal and emotional expression (8 items). Two items are not scored as part of these 3 subscales. A degree of limitation is rated on a 0-10 scale from 0 ("no limitation") to 10 ("severe limitation") [36, 37].
- Oral Behaviors Checklist (OBC). Evaluates parafunctional behaviors and generates a single scale representing the frequency of 21 activities such as clenching, chewing gum, and holding objects between teeth, yawn [38, 39].

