12.4 Final Analysis Plan

The main goal of the statistical analyses is to estimate change in study primary and secondary endpoints to evaluate efficacy of Erenumab. Intention to treat analysis will be performed using a within-subjects student's pair t-test or repeated measures ANOVA (if more than two time points) to determine significant reduction in pain after drug intervention in each patient. Subsequently, a between-subjects unpaired t-test or two-way mixed designed ANOVA (if more than two time points) will be performed to determine difference between the placebo and erenumab groups. *Post-hoc analysis* will only be conducted following a significant ANOVA test, to protect from Type I errors. We will use a 2-way between subject's repeated measure ANOVA design to determine difference between the Erenumab group and placebo group, or a between-subjects unpaired t-test if two groups only. We will also use student's paired t-test to determine time points of significance. 50% reduction in pain days will be determined as a function of baseline pain days. Where, appropriate similar statistical procedures will be used for secondary endpoints.

Descriptive statistics for safety measures will also be calculated.

We will collect the following data for descriptive purposes and, if necessary, to use as covariates: Demographic information (age and race/ethnicity), rescue medication history, psychological factors and perceived change in overall status (PGIC).

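### The primary pain score is withheld below 80% diary compliance and has no fallback, so the analysis as written is not the intention-to-treat analysis that section 12.4 states

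*Combined protocol and SAP*

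**What the plan says.** - Section 3.2.1 defines the primary score as the mean of daily diary ratings at baseline, then "for each month/cycle (4 weeks/28 days) during the 12 weeks (3 cycles) of treatment", and again for the month before the last visit. It then sets the condition: "The monthly mean pain intensity score will be calculated if a participant has at least 80% compliance with the DSD".
- Section 8.1 repeats the expectation, "Participants should have at least 80 % compliance with the DSD", without saying what happens to data that fall short. It also says that "a new form will be used for each month of the study".
- Sections 7.3.2 to 7.3.4 list "Assess compliance with Daily Symptom Diaries" as a task at Visits 2, 3 and 4.
- Section 4, inclusion criterion 6 in 5.1, and 7.2.1 use the same 80% as an entry condition for the baseline period, before randomisation.
- Section 12.3.2 gives the endpoint as the change from Visit 0 to Visit 4, using average pain in the month before the visit.
- Section 12.4 states: "Intention to treat analysis will be performed using a within-subjects student's pair t-test or repeated measures ANOVA". The comparison between arms is then an unpaired t-test or a two-way mixed ANOVA.
- None of these sections defines the intention-to-treat set, a rule for a month below 80%, an imputation method, a likelihood-based model or a sensitivity analysis.

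**The concern.** As an entry condition, 80% compliance is sound: it acts before randomisation and cannot unbalance the arms. Section 3.2.1 applies the same threshold to months after randomisation. There, missed entries may be related to pain, side effects or loss of interest, any of which treatment could influence. A patient without a score cannot enter a t-test or a complete-case ANOVA, so the patients compared would be partly selected by their behaviour after randomisation.

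Two things are at stake in a trial of 60 patients. One is precision: diary data already in hand are set aside. The other is the protection that randomisation gives to the comparison of arms, which is what an intention-to-treat analysis is meant to preserve. The 15% allowance in section 12.2 is for drop-out at follow-up and does not mention patients who stay in the study but miss the diary threshold.

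**Working it through.** **1. The cut-off.** The inputs are the 80% threshold and the 28-day month (both 3.2.1). The plan gives no day count to reproduce.
- 0.80 x 28 = 22.4, so 23 entries are needed.
- 22/28 = 78.6% fails; 23/28 = 82.1% passes.

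This assumes that compliance is counted per month. If it were counted over the 84 treatment days, 0.80 x 84 = 67.2, so 68 entries would be needed. A patient with 67 (79.8%) would then have no treatment-month score at all.

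**2. What a missing score does under the named methods.**
- Unpaired t-test on change from Visit 0 to Visit 4 (12.3.2, 12.4): the patient is lost if the month before Visit 4 falls below the threshold.
- Repeated-measures or mixed ANOVA on complete cases: the patient is lost if any analysed month falls below it.

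**3. Illustrative cost in precision.** The documents give no compliance rate, so the shares below are assumed. With a share p lost equally from both arms and an unchanged SD, the standard error is multiplied by 1/sqrt(1 - p).

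| p lost | Patients left of 60 | SE multiplier |
|---|---|---|
| 5% | 57 | 1/sqrt(0.95) = 1.026 |
| 10% | 54 | 1/sqrt(0.90) = 1.054 |
| 20% | 48 | 1/sqrt(0.80) = 1.118 |

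If all three treatment months are required and failures are independent between months, the same rates per month leave 60 x 0.95³ = 51, 60 x 0.90³ = 44 or 60 x 0.80³ = 31 patients. If the same patients fail every month, the loss is that in the table. Partial clustering falls between the two.

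**4. What a partial month costs.** Assume a between-patient SD of 20 and a day-to-day SD of 15 (neither is in the documents), with scattered gaps and independent days. The SD of the difference between a k-day mean and the 28-day mean is 15 x sqrt(1/k - 1/28).
- k = 22: 15 x sqrt(1/22 - 1/28) = 1.48 points. Added variance is 1.48²/20² = 0.5%.
- k = 14: 15 x sqrt(1/14 - 1/28) = 2.83 points. Added variance is 2.83²/20² = 2.0%.
- If the 14 days are the first half of the month and the day-to-day correlation is 0.4, simulation gives 4.12 points. Added variance is 4.12²/20² = 4.2%.

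**5. Where a partial month misleads.** Suppose pain falls linearly by D points from day 1 to day 28. Days 1 to 14 centre on day 7.5 and the whole month on day 14.5. The half-month mean is then too high by (14.5 - 7.5) x D/27 = 7D/27, about a quarter of D.

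**The case against.** Several points on the other side stand.

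- **The period is not stated.** Section 3.2.1 does not say that 80% applies in each month. The monthly reading fits the monthly scores, forms and visit checks, but it remains a reading. Counting over the whole treatment period would not help, since a failing patient would then lose every treatment-month score.
- **No sentence orders exclusion.** A reader might infer that the plan deliberately removes these patients. The documents do not say so. The loss follows from having no score and no missing-data method, and which patients are lost depends on an analysis that 12.4 leaves open. A Statistical Analysis Plan listed under Supplemental Materials is stored apart from the protocol and could address this. It is not among the documents, and 3.2.1 would still hold the rule.
- **A large loss is not shown.** A reader might infer that a sizeable part of the sample disappears. Every randomised patient has already met 80% at baseline, and compliance is checked at visits, so failures may be few. Patients with no diary data in a month cannot be given a score for it under any rule.
- **Non-replacement is a different matter.** Section 5.5.2 says "Participants withdrawn after randomization will not be replaced". It concerns withdrawal. A patient who stays in with 22 diary days has not withdrawn, so that sentence does not bear on this point.
- **Partial months are not harmless.** If missed days depend on pain, partial-month means can be biased too, and the variance figures in step 4 do not capture that.

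These points limit the size of the problem and shape the remedy. They do not supply the missing rule.

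**Conclusion.** The point holds in a limited form. Section 3.2.1 makes the primary score depend on 80% diary compliance after randomisation. On the per-month reading, 22 of 28 days gives no score. The documents provide nothing to put in its place, and the methods named in 12.4 then drop the patient: from the t-test if the month before Visit 4 fails, and from a complete-case ANOVA if any month fails. The intention-to-treat statement in 12.4 is therefore not met by the analysis described.

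The size is unknown. Losses of 5%, 10% or 20% would raise the standard error by about 3%, 5% or 12%, but these shares are illustrations and not estimates. Bias between arms is possible, and neither its direction nor its amount can be derived from the documents. The change is cheap enough to make without knowing either.

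**What to change.** - In 3.2.1, state that 80% compliance is the entry condition for the baseline period only. For each month after randomisation, calculate the mean from all recorded diary days, or from a low stated minimum. Any minimum is a judgement, and the documents give no basis for a particular number.
- In 12.4, define the analysis set as all randomised patients. Name a likelihood-based mixed model for repeated measures on the monthly scores as the primary method, so that a patient with a missing month stays in through the other months.
- Report the analysis restricted to months with at least 80% compliance as a sensitivity analysis, and state the period over which compliance is counted.

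The cost is a few sentences and one extra analysis, with no new data collection. The mixed model assumes that missing months are explained by the observed scores. Partial-month means are slightly noisier (about 0.5% more variance at 22 days and 2% at 14 days, on the assumptions in the working), and more so with fewer days. They can also be biased if missed days relate to pain or if pain trends within the month. The sensitivity analysis helps to examine this but does not remove it.

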3.2.2 Secondary

Efficacy will be investigated further using secondary outcomes:

TMD pain days: Percentage of participants with at least a 50% reduction from baseline in monthly TMD pain days. Time Frame: Baseline phase, the 12 weeks of management and until Visit 4.

Definition of TMD pain day: A TMD pain day was any calendar day in which the participant experienced pain, stiffness, soreness, tenderness, in the jaw or temple area or either side being brief or continuous; and/or pain with TMJ biomechanics (chewing, mouth opening or any jaw movement; and/or pain with jaw activities (yawning, kissing, talking); and/or pain with jaw habits (chewing gum, clenching, grinding).

At least a 50% reduction from baseline in monthly TMD days will be determined if the change in monthly TMD days from baseline phase through the 12 weeks treatment phase (3 cycles) * 100 / baseline monthly TMD days less than or equal to -50%.

Functional measures related to TMJ biomechanics and pain related behaviors:

TMD examination and Jaw functional limitation Scale: Change related to TMJ biomechanics/Jaw function and symptomatology in response to TMD examination.

Oral Behaviors (OBC): Changes in parafunctional behaviors

Pressure Pain Thresholds: Changes in myalgia and arthralgia

Graded Chronic Pain Scale (GCPS): Changes in pain intensity and pain related disability

Patient Global Impression of Change (PGIC): Assesses patient perspective of pain improvement

Hospital Anxiety and Depression Scale: Evaluation of Anxiety and depression

Exploratory Endpoint

To investigate the efficacy of Erenumab in decreasing pro-inflammatory cytokine release

4 STUDY DESIGN

60 patients (30 per each arm) aged 18-65 years old of either sex, and any race or ethnicity presenting chronic painful temporomandibular disorders (TMD) will be randomly assigned in a 1:1 parallel, double-blind, phase 2 single center clinical trial, to receive either Erenumab or placebo. Participants will attend 6 clinic visits (Visit 0-Visit 5) over a period of 21 weeks. The study should be completed over a period of 3 years, with an estimated duration of recruitment of 2.5 years.

Participants will be pre-screened in person at the Brotman Facial Pain clinic, the Oral and Maxillofacial Surgery Clinic both at the University of Maryland, School of Dentistry or by telephone. Potentially eligible and interested participants will be scheduled for a Screening and Baseline Visit (Visit 0). During Visit 0, participants will provide informed consent and be evaluated for eligibility; information including demographics, medical history, concomitant medications, and therapies will be collected. In addition, participants will be assessed for pain level, pain symptoms, jaw function, health status, among other measures and a blood sample will be collected. Procedures will include clinical examinations and tests and the dispensation of various questionnaires, all of which are listed in the Schedule of Events (Appendix A).

Participants who show compliance with the Daily Symptom Diary of at least 80% and who meet the pain score (inclusion criteria) for 28 days/4 weeks (baseline period) after Visit 0, will be randomly assigned to one of two groups (Erenumab or placebo) and will be scheduled for Visit 1 within a week of randomization.

At Visit 1, randomized participants will receive the 1st cycle of management and begin a 12-week drug treatment/placebo phase that will be divided into once a month injection/cycle for a total of 3 cycles. During that period, Visits 2-4 will take place, and many of the baseline assessments will be repeated. Between visits, communication will be conducted by telephone. The final study visit, visit 5, will occur 4 weeks after the last assessment (visit 4) and 8 weeks after the last dosage of drug treatment (Visit 3).

The primary endpoint will be the change in a monthly mean pain intensity score derived from the Daily Symptom Diary. Efficacy will be evaluated as the difference between Erenumab arm and the placebo arm in the monthly pain intensity score (on a 0-100 scale) during the 12 week treatment period.

5 STUDY ENROLLMENT AND WITHDRAWAL

The study is planning to enroll a total of 60 subjects that will be randomly assigned to one of the two study groups. It is anticipated that a total of 300 subjects will be screened in order to meet recruitment goals.

Vulnerable subjects: No specific vulnerable populations are being targeted for recruitment for this study.

5.1 Subject Inclusion Criteria

In order to be eligible to participate in this study, an individual must meet all of the following criteria:

1. Provide signed and dated informed consent form
2. Is between 18 and 65 years of age (inclusive; male or female and any race or ethnicity)
3. Meets diagnostic criteria for TMD: Myalgia with or without arthralgia
 - The participant must meet 2 criteria relating: 1) reported pain, ache or tenderness in the face, jaw/mandible, pre-auricular area, inside the ear or temple that it is modified by TMJ biomechanics. 2) finding(s) of TMD myalgia according to the classification DC/TMD criteria.
4. Has experienced facial pain and/or pain with TMJ biomechanics for the last 3 months episodically or unremitting
5. Has experienced facial pain for at least 10 days of the last 30 days prior to Baseline Visit (Visit 0)
6. Prior to randomization, has been compliant 80% with the entries in the Daily Symptom Diary within the baseline period and reported an average pain level ≥ 30 on a numerical rating scale (0-100) in the DSD, or has experienced a pain level ≥ 30 on the same scale for at least 3 days in the week prior to Visit 1.
7. If taking a prescription medication daily for the management of pain (taken for at least 30 days before baseline), agrees to continue the daily use of the medication throughout the study at the same dosage.

8. If taking prescription medication, opioid medication or OTC medications as needed or episodically for the management of TMD pain agrees to discontinue its use prior to the Screening and Baseline Visit.
 - Rescue medications will be defined as allowable over-the-counter analgesics used for treatment of TMD pain. In case a patient presents pain during the study, only it is allowed the use of OTC medications as a “rescue” and as described on section 6.6.3: Participants use of short-acting non-prescription analgesics such as NSAIDs, acetaminophen or aspirin during the study, will be recorded and quantified at each visit, and the usage will be classified as either episodic or daily. Episodic use of non-prescription analgesics will be defined as use for no more than 2 consecutive days and for no more than 18 days from baseline to visit 4.
 - This type of analgesics should not be used for more than 2 days a week prior to Baseline and a week prior to visit 4, when the exploratory outcome is assessed (cytokine release assay).
9. If taking OTC pain medications daily agrees to continue its daily use at the same dosage throughout the study.
 - If a participant is taking an over-the-counter medication daily for management of other type of pain or for prophylaxis of myocardial infarction or stroke, the participant will be encouraged to continue the same usage of that medication throughout the study.
10. Agrees to not start any new prescription medication for the management of pain throughout the study
11. Agrees to not start any injection therapy for the management of TMD (trigger point injections, steroid injections, Botox) during the course of the study
12. Agrees to not use acupuncture for the management of pain during the course of the study
13. Agrees to not have Physical therapy for the management of TMD during the course of the study.
14. Agrees to not start intraoral appliance therapy during the course of the study. If the patient has used a nightguard for more than one month before the study, agrees to continue use it only at night.

15. Females of childbearing potential agree to use one of the following methods of contraception throughout the study: licensed hormonal method, intrauterine device, female or male condoms with contraceptive foam, abstinence, bilateral tubal ligation/occlusion, or vasectomy in partner (if postmenopausal, must not have menstruated for at least 12 consecutive months)
16. Willing and able to understand and comply with all study procedures and be available for the duration of the study

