7.2.1 Randomization

Prior randomization, the participant to be eligible is required to have 80% compliance with the Daily Symptom Diary for the baseline period after visit 0 and reported an average pain level ≥ 30 on a numerical rating scale (0-100) or had experienced a pain level ≥ 30 on the same scale for at least 3 days the week before randomization. Participants then will be randomly assigned to one of two groups (Erenumab or placebo) and will be scheduled for Visit 1. Visit 1 should be scheduled within a week after randomization

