12.2 Sample Size Considerations

The proposed sample size of 60 randomized patients split into two independent groups is based on a 30-50% reduction in TMD pain scores at follow-up, assuming a power of 90%, alpha = 0.05, assuming a 0.5 (medium) effect size. This was calculated using GPower software. This sample size is also based on the conservative assumption of a 15% patient drop out at follow up.

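### The 'or' in inclusion criterion 6 admits patients with a baseline monthly mean below 30, which dilutes the primary comparison; baseline pain is neither a stratification factor nor a covariate

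*Combined protocol and SAP*

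**What the plan says.** Criterion 6 in 5.1 gives two ways to meet the pain requirement. The first is that the patient "reported an average pain level ≥ 30 on a numerical rating scale (0-100) in the DSD". The alternative is "or has experienced a pain level ≥ 30 on the same scale for at least 3 days", counted in the week before Visit 1. Section 7.2.1 repeats the choice but ties it to a different week: the patient "had experienced a pain level ≥ 30 on the same scale for at least 3 days the week before randomization".

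Section 3.2.1 defines the primary endpoint as a change from baseline in a monthly score, "representing the arithmetic mean of daily average pain intensity score values". Section 4 says the diary compliance and pain score conditions apply "for 28 days/4 weeks (baseline period) after Visit 0". Section 12.2 says the sample size "is based on a 30-50% reduction in TMD pain scores at follow-up", with an effect size of 0.5, 90% power, alpha 0.05 and 15% dropout.

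Criterion 4 admits pain that is episodic or unremitting. Criterion 5 asks for 10 pain days in the 30 days before Visit 0. Neither sets an intensity. Section 5.4.1 describes blocked 1:1 randomisation by IDS and names no stratification factor. The covariates that 12.4 would use if necessary are demographics, rescue medication history, psychological factors and PGIC; baseline pain is not among them.

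**The concern.** The two limbs are not equivalent. The first puts a floor of 30 under the quantity that the primary endpoint measures. The second looks at three days of one week and leaves the rest of the baseline month open, so the floor disappears for anyone who qualifies that way. A patient with a low baseline mean can lose only a few points, however well the drug works. Mixing such patients with patients well above 30 lowers the average absolute difference between arms and adds between-patient variation that the planned t-test or ANOVA does not remove.

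**Working it through.** **The plan's own figure.** A two-sided two-sample t-test at d = 0.5, alpha 0.05 and 90% power needs 86 per arm, so 172 in all, or 172/0.85 = 203 after 15% dropout. The planned 30 per arm gives 47.8% power at d = 0.5. That the 60 does not follow from the stated inputs is a separate point. It matters here because it leaves little margin for dilution.

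**Lowest baseline means that the second limb allows.** Take three days at exactly 30 and let the other 25 days average x. The 28-day mean is (3 × 30 + 25x)/28.

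| Other 25 days average | Baseline mean |
|---|---|
| 0 | 90/28 = 3.2 |
| 10 | 340/28 = 12.1 |
| 20 | 590/28 = 21.1 |
| 29 | 815/28 = 29.1 |

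With the minimum diary compliance (23 of 28 days) the lowest value is 90/23 = 3.9. Appendix A gives 1-3 weeks between Visit 0 and Visit 1. On that basis the lowest value is 90/21 = 4.3 (three weeks) or 90/7 = 12.9 (one week).

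**Room to improve.** A 30-50% reduction is 9-15 points from a mean of 30, 6.3-10.6 points from 21.1, and 1.0-1.6 points from 3.2.

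**Dilution, with assumed inputs.** None of these inputs is in the documents.
- First-limb baselines: normal, mean 50, SD 15, cut at 30, which gives a mean of 52.7.
- Second-limb-only baselines: uniform from 4 to 30, mean 17.
- Placebo falls 25%, and erenumab a further 30% of the remainder. The arm difference is therefore 0.75 × 0.30 = 0.225 of baseline.

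Before any limit at 0, the expected differences by second-limb share are:
- 0%: 0.225 × 52.7 = 11.9 points
- 20%: 0.225 × (0.8 × 52.7 + 0.2 × 17) = 10.2 points
- 40%: 0.225 × (0.6 × 52.7 + 0.4 × 17) = 8.6 points

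Simulating follow-up scores with a residual SD of 20, held at or above 0, lowers the first two to about 11 and 9.6. Either way, a 20% share removes about 14% of the difference (10.2/11.9 = 0.86).

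**Power in the same simulation (30 per arm, unadjusted t-test, SD 20):** about 58%, 45% and 33% at shares of 0%, 20% and 40%. At a 20% share, adding the stratum to the model raises power from 45% to 49%. With SD 15 it rises from 65% to 72%, against about 80% with no second-limb patients.

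**Near-worst case.** Suppose every second-limb patient sits at 3.2, other patients respond as from 30, and the SD is unchanged. Then d = 0.5 × [(1 − q) + q × 3.2/30]. For q = 10%, 20% and 30%, d is 0.455, 0.411 and 0.366, and power falls from 47.8% to 41.1%, 34.6% and 28.6%.

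**The case against.** A reader might infer that patients with a mean near 3 will be typical and that they have almost no room to improve. The documents do not support that. A mean of 3.2 needs 25 of 28 diary days at exactly 0. Criteria 4 and 5 do not exclude such a patient, because they set no intensity and look at an earlier period, but they make one unlikely. The figure also depends on the 28-day baseline. It should be read as a bound.

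A reader might also infer that the second limb is an error to be deleted. Criterion 4 deliberately admits episodic pain, and the secondary endpoint on TMD pain days suits such patients. Section 5 already expects 300 screened for 60 enrolled at one centre, and the extra screen failures from deletion are unknown. Deletion is a trade-off about population and recruitment.

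Chance imbalance between arms might be read as bias. It is not: randomisation covers it and the test's error rate allows for it. Arms of 30 would differ by six or more second-limb patients in 7.5% of trials at a 20% share and 14.7% at 40%. With the inputs above and a placebo-type fall, a six-patient imbalance shifts the mean change by (6/30) × 0.25 × (52.7 − 17) = 1.8 points. That is avoidable noise.

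Finally, the loss is smaller if the drug effect is a fixed number of points. With 10 points and SD 20, which is the plan's d = 0.5, a 20% share lowers power only from about 48% to 44%. All of these objections limit the size. None restores the floor of 30 or supplies an adjustment for baseline pain.

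**Conclusion.** The point holds as a moderate, inexpensive design weakness. The text admits patients with a baseline monthly mean below 30, the primary endpoint is the change in that mean, and the plan neither stratifies by baseline pain nor adjusts for it. The direction, a smaller absolute difference and more baseline heterogeneity, follows whenever the achievable change grows with baseline. The size cannot be fixed from the documents. At an assumed 20% share, the arm difference falls from about 11 to 9.6 points under a proportional effect. The power loss then ranges from about 4 percentage points (fixed 10-point effect) to about 13 (proportional effect, SD 20: 58% to 45%). All of these figures rest on the assumed share, baseline distributions and SD.

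**What to change.** - **5.4.1:** have IDS stratify the existing blocked list by baseline-period diary average, 30 or more versus below 30. The value is available before randomisation once the baseline period is fixed.
- **12.4:** include the baseline mean pain score, or at least the stratum, as a prespecified covariate in the between-arm primary analysis.
- **Reconcile the text so that the stratum can be determined in time.** Criterion 6 uses the week before Visit 1 and 7.2.1 the week before randomisation, while Visit 1 may fall up to a week after randomisation. Sections 4 and 7.2 give a 28-day or 4-week baseline. Appendix A gives 1-3 weeks, and its footnote B refers to one week after Visit 0. Section 5.4.1 puts randomisation within 7 days after Visit 0. Criterion 6 should also say whether the 80% compliance condition binds both limbs.

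The cost is a short amendment, one more randomisation list and one model term. Recruitment is unaffected. This balances the low-baseline patients and removes some variance, but they still have less room to improve, so it recovers only part of the lost power. Whether to remove the three-day limb is for the sponsor to weigh against recruitment and the intended population; this point does not require it.
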